6 STUDY INTERVENTION

6.1 STUDY INTERVENTION(S) ADMINISTRATION

6.1.1 STUDY INTERVENTION DESCRIPTION

Ketamine:

Ketamine is widely available as an anesthetic agent under the brand name Ketalar, for use in emergency rooms and hospital settings for sedation and analgesia. The typical sub-anesthetic dose in clinical trials for patients with TRD or PTSD is 0.5 mg/kg, administered intravenously over 40 minutes.

Relevant to the criteria for an exemption in § 312.2(b), we informally reached out to the Food and Drug Administration (FDA) via email seeking their advice regarding the IND exemption. We were informed that the Division of Psychiatry Products is currently exempting studies with 3 or fewer intravenous infusions of subanesthetic doses of ketamine. As our proposed project involves 6 infusions, we will proceed with an IND submission. The PI, [name], and Co-Is Drs. [name] and [name] have extensive

experience in obtaining IND exemptions for ketamine trials. No subject will be enrolled in the proposed study until an IND exemption has been granted.

Relevant to the individual criterion for exemption in § 312.2(b) (bolded statements from FDA guidance):

- 1. The drug product is lawfully marketed in the United States.** We propose to use ketamine that is commercially available and will be supplied by our research pharmacy, the Investigational Drug Service at the Icahn School of Medicine at Mount Sinai.
- 2. The investigation is not intended to be reported to the FDA as a well-controlled study in support of a new indication and there is no intent to use it to support any other significant change in the labeling of the drug.** We do not intent to report the results of our proposed study to the FDA as a well-controlled study in support of a new indication, nor do we intend to use it to support any other significant change in the labeling of the drug. As mentioned earlier, the purpose of this study is to evaluate whether the addition of Written Exposure Therapy to a course of ketamine infusions can extend the effect of ketamine on PTSD symptoms in individuals with chronic PTSD who respond to ketamine.
- 3. The investigation is not intended to support a significant change in the advertising for the drug.** We do not intend to utilize the data we generate to support any changes in advertising of ketamine. As mentioned in the specific aims section, the purpose of this study is to evaluate whether the addition of Written Exposure Therapy to a course of ketamine infusions can extend the effect of ketamine on PTSD symptoms in individuals with chronic PTSD who respond to ketamine.
- 4. The investigation does not involve a route of administration, dose, patient population, or other factor that significantly increases the risk (or decreases the acceptability of the risk) associated with the use of the drug product (21 CFR 312.2(b)(1)(iii)).** We intend to use ketamine via intravenous route (after diluting it with normal saline for total infusion volume of 100 mL) in adults with PTSD who are medically stable and have no medical contraindications against ketamine administration, three times per week for two weeks (total of 4 or 6 infusions over 2 weeks, depending on ketamine response). Previous reports have used repeated infusions of ketamine (up to 6) over a two-week period, including our recently completed randomized controlled trial of repeated ketamine infusions in patients with chronic PTSD, compared to the active placebo midazolam (PI of the proposed study, [name], was the PI of that trial, funded in part by a NARSAD Independent Investigator Award from the Brain & Behavior Research Foundation).
- 5. The investigation is conducted in compliance with the requirements for review by an IRB (21 CFR part 56) and with the requirements for informed consent (21 CFR part 50).** We plan to enroll subjects after the study is approved by the Institutional Review Board at Mount Sinai and after individual subjects have provided informed consent.
- 6. The investigation is conducted in compliance with the requirements of § 312.7 (i.e., the investigation is not intended to promote or commercialize the drug product).** We do not intend to promote or commercialize the drug product (ketamine) with this investigation.

Written Exposure Therapy:

Written Exposure Therapy (WET) is a brief evidence-based treatment for PTSD, developed by our collaborator and study consultant [name] (Boston University). WET will be administered by trained therapists, under the supervision of [name].

6.1.2 DOSING AND ADMINISTRATION

Ketamine:

The dose of ketamine at each infusion is fixed at 0.5mg/kg mg, and up to 60 mg per infusion (regardless of body weight), to be administered intravenously over 40 minutes. Individuals at or above 120 kg will receive 60 mg over 40 minutes. Ketamine infusion will be discontinued earlier if necessary due to side effects as described below:

1. Changes in psychiatric symptoms at any time during the study:
 - a. Treatment-emergent mania, hypomania, worsening suicidality or psychosis
2. Emergent medical symptoms on the infusion days:
 - a. Criteria for stopping the infusion:
 - i. Any change in mental status resulting in inability to respond to verbal stimuli.
 - ii. Severe headache, or severe anxiety, or other patient tolerability issues
 - iii. SBP >180, DBP >110 on 2 consecutive readings, ~5 min apart
 - iv. HR >120 for 5 minutes
 - v. RR< 6, SPO2 <90% at any time point
 - vi. Should the patient's vital signs deviate from normal, the clinician may temporarily pause the infusion until the vital signs/mental status have returned to normal, and subsequently resume the infusion at the same or slower rate. Recommended protocol: If 150 ml/h not tolerated, slow to 100 ml/h; If 100 ml/h not tolerated, slow to 50 ml/h.
 - b. During intravenous infusion day and post-administration monitoring period: in the event of tachycardia >110 beats per minute, systolic BP>160 mm Hg or diastolic BP>100mg Hg that is not resolved by pausing or slowing the rate of infusion, the study physician will treat using the following preferred medications:
 - i. Esmolol 100-500 mcg/kg IV titrated to reduce the heart rate and systolic BP.
 - ii. Nitroglycerin 20-80 mcg IV titrated to reduce the BP to an acceptable range.
 - iii. Further therapy with longer acting agents such as metoprolol, esmolol and labetalol will be administered if the response to initial therapy is not adequate.
 - c. If three consecutive vital sign measurements (over 15 minutes) are consistently above the HR and BP limits stated above despite therapy, intravenous infusion will be discontinued.
 - d. If a patient becomes sedated to the point that he/she is unresponsive to verbal commands or there is complete or partial airway obstruction, intravenous infusion will be discontinued. The patient would then be transferred to the Post Anesthesia Care Unit or an intensive care unit bed as necessary for further observation and treatment.

- e. In the event that $\text{SpO}_2 < 95\%$ over 5-minute interval, the study physician will have the option of inserting a nasal cannula or adjusting the flow rate. If the SpO_2 does not increase to 95% or greater with intervention, the study will be discontinued and further therapy will be administered by the study physician.
- f. In the event of a respiratory or cardiac arrest, Team 7000 will be called.

Procedures Related to Ketamine Administration:

Ketamine Infusion: All infusion procedures and monitoring will take place at the Psychiatry Infusion Suite, Icahn School of Medicine at Mount Sinai (ISMMS), using the existing Standard Operating Procedures that are in place for the administration of ketamine in research studies. All eligible participants will receive **six infusions**, administered three times per week over two consecutive weeks. At each infusion, participants will receive 0.5 mg/kg racemic ketamine hydrochloride, the same dose administered in prior studies of ketamine for the treatment of PTSD.^{6,49} An indwelling catheter will be placed in the antecubital vein of the non-dominant arm, and pulse, blood pressure, digital pulse-oximetry, and ECG monitoring will be instituted. All physiologic monitoring data will be recorded on a standard anesthesia record beginning five minutes prior to ketamine administration. Co-Investigator [name] or another study- affiliated physician with privileges to administer ketamine will be present at the Psychiatry Infusion Suite throughout the administration of ketamine so that potential adverse events can be evaluated and treated promptly. A medical crash cart is available for emergencies. [name] or another study-affiliated physician will remain available until at least one hour following the termination of the study drug infusion or until the patient meets Aldrete criteria (good respiration, O₂ saturation, consciousness, circulation, and activity) for post- anesthesia care, whichever period is longer. Blood samples will be collected from participants during the first infusion for measurement of plasma ketamine and norketamine levels.

Assessment of response to ketamine after four initial infusions: Response to ketamine is defined as $\geq 30\%$ reduction in PTSD symptom severity from baseline (prior to any infusions) determined with the CAPS-5, administered to the participant by a trained clinical rater 24 hours following completion of the fourth infusion. This degree of improvement is commonly used in clinical trials in individuals with PTSD to represent clinically significant improvement,^{62,64,77} and was also used in our recently completed RCT of repeated ketamine for PTSD.⁴⁹

WET:

Procedures Related to WET Administration:

WET will be delivered using a structured manual to ensure fidelity. Therapists will be trained Master's- or PhD-level licensed mental health providers, supervised by study consultant [name]. WET will be delivered remotely by therapists to participants in their homes, via a secure HIPAA- compliant video telehealth platform, using methods implemented before the COVID-19 pandemic and further developed during the pandemic by [name] and colleagues.⁶⁵ WET will be administered over a total of 2 weeks. Week 1: The first two sessions of WET will be delivered interleaved with the last two ketamine infusions (each WET session and ketamine infusion occurring on a different day, i.e., four different days). The ketamine dose and administration protocol will be the same for all six infusions. Week 2: The last three sessions of WET will be delivered during the second week post-WET start.

Delivery of WET:

WET will be delivered using a structured manual to ensure treatment fidelity. Therapists will be mental health providers at Mount Sinai. We anticipate that there will be between one and three therapists in this study, who will be assigned to individual participants for the duration of their participation.

WET consists of 5 sessions, with the first session lasting 1 hour and each subsequent session lasting approximately 40 minutes. The first session includes psychoeducation about common trauma reactions and the treatment rationale, presented by the therapist. The participant is then given general instructions for completing the trauma narratives and specific instructions for completing the first 30-minute narrative writing session. All WET sessions begin with the therapist reading the specific writing instructions, clarifying any questions the participant might have, and leaving the instructions with the participant during the 30-minute writing session. Writing instructions begin with a focus on the details of the trauma and then shift to the meaning of the trauma event. After 30 minutes of writing, the therapist stops the writing and conducts a 5-10 minute check-in regarding how the writing session went for the participant.

Training and Supervision of Therapists and Treatment Fidelity:

Following established procedures used clinical trials of WET,^{40,41} therapists will be trained and supervised by [name]. Therapists will attend a four-hour WET training workshop led by [name], followed by completion of at least two cases of WET supervised by [name] that are completed with competency as determined by the supervisor. Therapists will be instructed on data collection during sessions and any required paperwork related to the proposed study. Treatment fidelity will be closely monitored to prevent drift.

Narratives from WET Sessions:

Participant narratives will be collected as part of the WET sessions, as they are a necessary part of treatment and are used to ensure that the instructions for each writing session are followed by the participants. Collection will be completed securely, either by uploading a picture of the narratives to the REDCap database, uploading a scanned copy of the narratives, or by participants delivering the narratives in person or by mail.

Procedures for Transition to Clinical Care at Study Completion:

At the time of initial screening, subjects will be asked to identify if they have a current mental health provider. For patients with a current provider, we will ask them to provide the name and contact information of this provider. Patients who are not eligible for study participation and do not have a current provider will be offered a referral for clinical care if appropriate. For patients who complete the study (including outcome assessments), a study clinician (PI or psychiatrist who is covering for the PI) will meet with them to discuss the transition of care plan. As part of the study exit visit, the study clinician will complete an end-of-study disposition form, which includes a description of the treatment plan and the next scheduled follow-up appointment with their provider, if applicable. This will be

documented in the participant's chart. For patients who have an established psychiatrist or other treatment provider, the study team will work closely to ensure that there is a smooth transition of care from the end of the study to their clinical treatment. A study clinician may contact the participant's primary provider for coordination of clinical care. For patients who do not have pre-established care, the study team will provide referrals to one of the programs currently serving individuals with PTSD, i.e., a referral within the Mount Sinai Health System or larger community, based on availability and patient preference. At the exit visit, the study team will check in on the status of the disposition plan, and any follow-up appointments will be discussed.

6.2 PREPARATION/HANDLING/STORAGE/ACCOUNTABILITY

6.2.1 ACQUISITION AND ACCOUNTABILITY

The study drug, ketamine, will be acquired, stored, and tracked by the ISMMS research pharmacy, Investigational Drug Services (IDS), in keeping with institutional policies. Full MOPs are available directly from IDS.

6.2.2 FORMULATION, APPEARANCE, PACKAGING, AND LABELING

This information will be provided by the ISMMS research pharmacy, IDS.

6.2.3 PRODUCT STORAGE AND STABILITY

This information will be provided by the ISMMS research pharmacy, IDS.

6.2.4 PREPARATION

This information will be provided by the ISMMS research pharmacy, IDS.

6.3 MEASURES TO MINIMIZE BIAS: RANDOMIZATION AND BLINDING

As this is an open-label pilot study, no randomization is required; all eligible participants will receive six ketamine infusions and participate in five WET sessions. No blinding is necessary, as all participants will receive the same treatment.

6.4 STUDY INTERVENTION COMPLIANCE

The primary study monitors, [name] and [name], will monitor study progress, compliance, and safety continuously. The two monitors will meet formally during a weekly lab meeting. In addition, the DSMB (see below) will review the accumulated safety and data information twice a year.

6.5 CONCOMITANT THERAPY

For this protocol, a prescription medication is defined as a medication that can be prescribed only by a properly authorized/licensed clinician. Medications to be reported in the Case Report Form (CRF) are concomitant prescription medications, over-the-counter medications and supplements.

6.5.1 RESCUE MEDICINE

The study site will supply the following medications, available emergently through the Psychiatry Infusion Suite or Clinical Research Unit or non-emergently through IDS:

- Naloxone (opioid reversal)
- Flumazenil (benzodiazepine reversal)
- Epinephrine, Ephedrine, Phenylephrine
- Esmolol, Metoprolol, Labetalol, Hydralazine
- Atropine
- Albuterol Inhaler
- Lidocaine, Amiodarone
- Hydrocortisone, Diphenhydramine
- Aspirin 81mg, Nitroglycerin Tab, Dextrose 25%
- Ondansteron

7 STUDY INTERVENTION DISCONTINUATION AND PARTICIPANT DISCONTINUATION/WITHDRAWAL

7.1 DISCONTINUATION OF STUDY INTERVENTION

Discontinuation from ketamine or WET does not mean discontinuation from the study, and remaining study procedures should be completed as indicated by the study protocol. If a clinically significant finding is identified (including, but not limited to changes from baseline) after enrollment, the investigator or qualified designee will determine if any change in participant management is needed. Any new clinically relevant finding will be reported as an adverse event (AE).

The data to be collected at the time of study intervention discontinuation will include the following:

- Symptom measures (e.g.,CAPS-5, MADRS, PCL-5, SDS)
- Global Clinical Severity and Improvement (CGI-S and CGI-I)
- End-Of-Infusion labs
- Safety data
- Concomitant medications
- Follow-up plan

7.2 PARTICIPANT DISCONTINUATION/WITHDRAWAL FROM THE STUDY

Participants are free to withdraw from participation in the study at any time upon request.

An investigator may discontinue or withdraw a participant from the study for the following reasons:

- Pregnancy
- Significant study intervention non-compliance
- If any clinical adverse event (AE), laboratory abnormality, or other medical condition or situation occurs such that continued participation in the study would not be in the best interest of the participant
- Disease progression which requires discontinuation of the study intervention
- If the participant meets an exclusion criterion (either newly developed or not previously recognized) that precludes further study participation
- Participant unable to receive a total of four or six ketamine infusions, or unable to participate in WET.

The reason for participant discontinuation or withdrawal from the study will be recorded on the Visit Check-list Case Report Form (CRF). Subjects who sign the informed consent form and begin study procedures but do not receive the study intervention may be replaced. Subjects who sign the informed consent form, and begin study procedures and receive the study intervention, and subsequently withdraw, or are withdrawn or discontinued from the study, will not be replaced.

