Eligible patients will receive a total of 6 ketamine infusions and 5 WET sessions. The primary outcome will be change in PTSD symptom severity assessed by the Clinician-Administered PTSD Scale for DSM-5 (CAPS-5) from baseline (before the first infusion) to 12 weeks from the start of WET. All participants will be assessed until week 12 following the start of WET. They will complete weekly assessments from baseline until 6 weeks from the start of WET, as well as assessments at 12 weeks from the start of WET. At other time points between 6 and 12 weeks, participants will be assessed weekly, or less frequently as tolerated. Although initial response to ketamine (PTSD and co-morbid depressive symptom improvement) will be assessed after the first four infusions (prior to starting WET), all participants will receive 6 infusions and 5 WET sessions regardless of their initial response to ketamine. Participants will be asked not to make any changes to any concomitant treatment (i.e., medication dosages, psychotherapy) during this period.

Thereafter, participants who remain improved at the 12-week time point (compared to baseline) will then receive additional monthly assessments up to 24 weeks or until loss of this improvement.

We will also evaluate whether extinction learning ability –assessed with a computerized extinction learning task– is associated with PTSD symptom improvement from baseline to 12 weeks from the start of WET. If demonstrated to result in significant and maintained PTSD symptom improvement, this novel combined treatment may represent a promising intervention for individuals with chronic PTSD, deserving further study.

Objectives:

Primary Objective: To evaluate the efficacy of adding WET to ketamine therapy in improving PTSD symptoms from baseline to 12 weeks from the start of WET, in individuals with chronic PTSD .

Secondary Objectives (exploratory): (1) To evaluate improvement in PTSD symptoms from baseline to 6 weeks, and on other measures from baseline to 6 weeks, and from baseline to 12 weeks; (2) To evaluate durability of PTSD symptom improvement beyond 12 weeks in patients who remain improved, up to 24 weeks; (3) To evaluate whether ketamine-induced change in extinction learning is associated with improvement in PTSD symptoms from baseline to 12 weeks from the start of WET.

Endpoints:

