1.3 SCHEDULE OF ACTIVITIES (SOA)

Procedures	Screening	Baseline	Ketamine Infusions	24 hour Follow-Up Visit	Assessment of Response to Ketamine	WET Sessions	Weekly Assessment Until 12 weeks	Monthly Assessment Until Loss-of-Response
	Day - 28 to 0	Visit 1a, Day 1	Visit 1a-9; Days 1, 3, 5, 8, 11, 12	Visit 1b, Day 2	Visit 5, Day 9	Visit 6-12, Days 10, 12, 16, 18, 22	Visits 10, 13-23, Days 12, 19, 26...	Visits 23-26, Days 33...
Informed consent	x							
Demographics	x							
Medical history	x							
SCID-5	x							
CAPS-5	x	x			x		x	x
MADRS	x	x			x		x	x
WTAR	x							
MoCA	x							
IES-R		x	x	x	x			
QIDS-SR		x	x	x	x			
PCL-5	x	x			x		x	x
MOS-5		x					x ¹	
CES		x					x ¹	
PACT		x					x ¹	
CTQ	x							
TLEQ	x							
SDS	x	x		x	x		x	x
HMS			x ²					
PIQ			x ²					
C-SSRS	x	x			x		x	x
CADSS		x	x					
BPRS		x	x					
YMRS		x	x					
Extinction Learning Task	x				x			
CGI	x	x	x	x	x		x	x
Concomitant medication review	x	x	x	x	x		x	x
PRISE	x	x	x	x	x		x	x

Adverse event review and evaluation	x	x	x	x	x	x	x	x
Physical exam (including height and weight)	x							
Vital signs	x		x					
Weight	x		x					
EKG	x							
Routine labs	x							
Plasma ketamine and norketamine levels			x ³					
Urine pregnancy test	x		x					
Urine drug screen (UTOX)	x		x					
Ketamine infusion (0.5 mg/kg)			x					
Written Exposure Therapy (WET)						x		
Complete Case Report Forms (CRFs)	x	x	x	x	x	x	x	x

¹Visit 14 and 23 only

²only at Infusions 1 and 2

³only at Infusion 1

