Secondary outcome measures (exploratory): The CAPS-5 will be administered weekly (beginning at baseline prior to the first ketamine infusion) until 6 weeks from the start of WET; thereafter, the CAPS-5 will be administered weekly as tolerated until 12 weeks; all participants will be administered the CAPS-5 at the 12-week time point. Participants who maintain PTSD symptom improvement after 12 weeks will be assessed monthly up to 24 weeks from the start of WET or until loss of improvement, by the blinded clinical rater. The PCL-5 and SDS (self-report scales), the MADRS (administered by the blinded clinical rater), and the CGI-S and CGI-Improvement scales (administered by a study psychiatrist or clinician) will be administered at the same time points until 12 weeks, and then monthly up to 24 weeks or until loss of improvement (See **3.1 Schedule of Activities**). The Quick Inventory of Depressive Symptomatology-Self-Report version (QIDS-SR)⁶⁶ and the Impact of Events Scale-Revised (IES-R),⁶⁷ both self-report scales, will be administered at baseline, 24 hours after the first infusion, at each infusion visit, and on the day of response to ketamine assessment, to capture any ketamine-related rapid changes in symptom levels. An abbreviated version of the Medical Outcomes Study Social Support Survey (MOS-SSS),⁶⁸ the Centrality of Event Scale (CES),⁶⁹ and the Perceived Ability to Cope with Trauma Scale (PACT)⁷⁰ will be administered at baseline (prior to any infusions) and again 3 weeks after the first WET session; data from these scales will be used for Aim-3 analyses.

Safety Assessments: Participants will be evaluated prior to each infusion by the PI or another study-affiliated psychiatrist; including review of vital signs, weight/BMI, drug and pregnancy tests, concomitant medications and adverse events. Participants will be monitored continuously during all ketamine infusions. On infusion days, side effects will be assessed with the Patient-Rated Inventory of Side Effects (PRISE) Adverse Event Visit Checklist,⁷¹ the Clinician-Administered Dissociative States Scale (CADSS),⁷² the Brief Psychiatric Rating Scale (BPRS) 4 items assessing positive symptoms,⁷³ and the Young Mania Rating Scale first item.⁷⁴

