4.4 END OF STUDY DEFINITION

A participant is considered to have completed the study if he or she has completed all phases of the study shown in the Schedule of Activities (SoA), Section 1.3. For all participants, the earliest end of study will be the 12-week follow-up assessment. For participants who remain improved at this 12-week assessment, the end of study will be their final follow-up visit (depending on time to loss of this improvement).

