9.4.3 ANALYSIS OF THE SECONDARY ENDPOINT(S)

- **Secondary Efficacy Outcomes (Exploratory):** In this early-phase study, analyses of secondary efficacy outcomes will be considered exploratory and hypothesis-generating. CAPS-5, PCL-5, MADRS, CGI and SDS scores will be collected weekly through 6 weeks after the start of WET from all

eligible participants, and thereafter until 12 weeks (up to weekly, as tolerated, ensuring assessment at the 12-week time point for all participants). All participants will be followed naturally for 12 weeks from the start of WET, in order to capture, descriptively, more gradual effects of WET and potential effects of the combination of ketamine + WET in all patients. Thereafter, they will be collected monthly through week 24 from start of WET or until loss of treatment response, for the subgroup of participants who demonstrate improvement on the CAPS-5 at the 12-week assessment. Aggregate scores prior to adding WET, during WET, and during the maintenance phase (weeks 3 onward) will be reported descriptively at each time point using the number observed, mean, standard deviation, median, and interquartile range. Individual patient trajectories on these measures will be plotted over time to explore treatment response and patterns in maintenance of response. Mean change in CAPS-5 scores from baseline and corresponding 95% confidence intervals, as well as the proportion of patients with $\geq 30\%$ improvement from baseline on the CAPS-5 will also be reported at each time point. In addition, linear mixed-effects models of these outcomes may be fit to compare mean scores over time. Mixed models will test for the inclusion of a random intercept for patient and fixed effects for week against a fixed intercept model using a likelihood ratio test after comparing each model fit statistic (i.e., Akaike information criterion, AIC) where the best fitting model is the model with the lowest corresponding AIC. Once fit is assessed, parameter interpretation will commence.

- **IES-R and QIDS-SR with past-24-hour recall** – collected only at baseline, before each ketamine infusion, 24 hours after the first infusion, and on the response to ketamine assessment day – will be examined descriptively.

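### Section 7.2 lets the investigator withdraw from the study participants who cannot complete ketamine or WET, although section 7.1 keeps them in follow-up to the week-12 CAPS-5

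*Combined protocol and SAP*

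**What the plan says.** Section 7.1 sets the default: "Discontinuation from ketamine or WET does not mean discontinuation from the study, and remaining study procedures should be completed". It also calls for symptom measures, including the CAPS-5, when treatment is stopped ("The data to be collected at the time of study intervention discontinuation will include the following").

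The week-12 visit is planned for everyone. Section 4.1 states that "all participants will be administered the CAPS-5 at the 12-week time point". Section 4.4 adds: "For all participants, the earliest end of study will be the 12-week follow-up assessment". Section 9.4.3 repeats the intention ("ensuring assessment at the 12-week time point for all participants").

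Section 7.2 says that an investigator may withdraw a participant from the study, not merely from treatment, for several reasons. One is "Participant unable to receive a total of four or six ketamine infusions, or unable to participate in WET". Two others are significant non-compliance with the intervention and disease progression that requires stopping it. Voluntary withdrawal has its own sentence, and adverse events and the participant's best interest have their own bullet. The reason for withdrawal is recorded, and treated participants who leave or are withdrawn are not replaced.

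On the treatment course, the synopsis says "all participants will receive 6 infusions and 5 WET sessions regardless of their initial response to ketamine", and section 6.3 agrees. Section 6.1.1, under the fourth IND-exemption criterion, still describes four or six infusions according to ketamine response.

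**The concern.** The event that section 7.1 says should not end follow-up, stopping ketamine or WET, is listed in section 7.2 as a ground for ending it. Safety exits and voluntary exits are provided for elsewhere. What this bullet adds is the option to stop assessing someone who could not complete treatment but may be willing and safe to be interviewed. Neither section says when the exception should override the default.

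At stake is who contributes to the only primary result, a mean CAPS-5 change with a 95% interval (section 9.4.2). Failure to complete treatment may be related to outcome. Section 9.4.2 has no rule for a missing week-12 score, and section 9.3 does not say which dataset feeds the primary mean. Sections 4.3 and 9.4.3 also foresee comparison with the completed ketamine trial, so the make-up of the group behind the mean matters.

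**Working it through.** **Reading the sections together.**

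1. Section 7.1 says what should happen after treatment stops; section 7.2 says what the investigator may do. An investigator who never uses the bullet complies with both, so there is no strict contradiction.
2. Section 7.1 does not itself name the week-12 CAPS-5. The link comes from its reference to remaining procedures, read with sections 4.1, 4.4 and 9.4.3.
3. That the bullet can reach a willing participant is an inference, supported by the separate sentence for withdrawal on request.
4. The trigger has two readings. Four infusions is still the point at which response is assessed and WET begins; six is the full course. Someone who received five infusions passes on the first reading and fails on the second. The matching wording in section 6.1.1 suggests a remnant of a design in which the number of infusions depended on response.

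**The plan's own figure.** Section 9.2 gives a half-width of 0.5 SD for 15 patients. The known-SD formula gives 1.96/√15 = 0.506, which agrees. The t-based value is t(0.975, 14)/√15 = 0.554.

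**Illustration of size.** The inputs are N = 15 (section 9.2) and no replacement (section 7.2). The rest is assumed: k = 1 to 3 withdrawn under these bullets, a gap of 0.5 to 1 SD of change between those retained and those withdrawn, and an observed-case mean. The documents give no rate of investigator withdrawal. Their nearest figures are for treatment dropout: 50% of 10 in the ketamine plus prolonged-exposure pilot, and 25–40% cited in section 2.1. These measure something else, and section 2.2 expects much less dropout with WET.

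The full mean is [(15 − k) × M_retained + k × M_withdrawn]/15, so

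shift = observed-case mean − full mean = (k/15) × (M_retained − M_withdrawn).

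| k | n left | Half-width, normal (SD) | Half-width, t (SD) | Shift, gap 0.5 SD | Shift, gap 1 SD |
|---|---|---|---|---|---|
| 0 | 15 | 0.506 | 0.554 | 0 | 0 |
| 1 | 14 | 0.524 | 0.577 | 0.033 | 0.067 |
| 2 | 13 | 0.544 | 0.604 | 0.067 | 0.133 |
| 3 | 12 | 0.566 | 0.635 | 0.100 | 0.200 |

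The shift takes the sign of the gap, which the documents do not give. The largest value is 0.200/0.635 = 0.31 of the t half-width at n = 12, or 0.200/0.566 = 0.35 of the normal one. The smallest is 0.033/0.577 = 0.06 of the t half-width at n = 14. Going from 15 to 12 widens the interval by 0.566/0.506 = 1.12 (normal) or 0.635/0.554 = 1.15 (t).

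**Timing for someone who never starts WET.** The endpoint is dated from the start of WET, so such a person has no week-12 date. The Schedule of Activities lists WET at "Visit 6-12, Days 10, 12, 16, 18, 22". Counting from Day 10 gives 10 + 42 = Day 52 and 10 + 84 = Day 94. The schedule's weekly assessments run Day 12, 19, 26 and so on, which extrapolates to Day 47 for the sixth and Day 89 for Visit 23. A fixed Day 10 anchor would therefore sit five days off that series, and it would ignore any delay in the infusions.

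**The case against.** A reader might infer that section 7.2 orders these participants out, or that it contradicts section 7.1. Neither is supported: the wording is permissive, and section 7.1 is itself guidance, backed by three statements that the week-12 assessment is for everyone. A reader might also call the four-or-six trigger meaningless. That goes too far, since four infusions remains the point at which WET starts; ambiguous is the accurate word.

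There is more to say for the plan. Reasons for withdrawal are recorded, and the DSMB receives six-monthly reports on retention and reasons for dropout (section 10.1.6). CAPS-5 data are due at treatment discontinuation and weekly to week 6, and mixed models may be fitted (section 9.4.3). For someone who never starts WET, no dated primary outcome exists to be lost; that is a separate gap in definition. The numerical harm also depends on an observed-case analysis that the plan does not specify, and 0.20 SD is the far corner of an assumed range. The analysis is descriptive, so no test decision turns on it.

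All of this limits the weight of the point. It does not remove it for participants who start WET and then stop: none of these safeguards supplies their week-12 score, and a score that was never collected cannot be recovered at analysis.

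**Conclusion.** The point stands as a modest design weakness. Section 7.2 permits loss of a planned primary assessment for a reason that section 7.1 treats as no bar to follow-up, using a trigger that no longer fits the treatment plan. The effect on the descriptive mean is unknown and probably small: about 0.03 to 0.20 SD in absolute size, conditional on the assumed number withdrawn, the assumed gap and an observed-case mean. A reader might conclude that the reported improvement will be inflated. The documents do not support that, because they give neither the number who would be withdrawn nor the direction in which their outcomes would differ. Priority is minor to moderate.

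**What to change.** - Delete the bullet on four or six infusions and WET from section 7.2.
- State that non-compliance, or disease progression requiring treatment to stop, ends only the affected component (ketamine or WET) and not follow-up.
- State that every participant who received at least one infusion stays scheduled for the week-6 and week-12 CAPS-5. The exceptions are withdrawal of consent and exit under the best-interest bullet, the exclusion-criterion bullet where it precludes further participation (both section 7.2), the C-SSRS rule (section 8.1) or the pregnancy rule (section 8.3.9). The exclusion-criterion exit has to be on the list; otherwise the new sentence would conflict with a bullet that remains.
- For a participant who never starts WET, count weeks from that participant's own planned first WET date, with the same visit windows as for everyone else, rather than from a fixed Day 10.

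The cost is a short amendment and a few CAPS-5 interviews with people who are off treatment. The change does not address voluntary withdrawal, loss to follow-up or the missing-data rule, which need separate attention.
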